3. UTI

Urinary tract infection is defined based on the results of urinalysis in which one of the following conditions is present: leukocyturia (found > 5 leukocytes per field view), positive bacteria, positive nitrite, and/or leukocyte esterase positive.

4. Urodynamic

Urodynamic examination used in this study consist of non-invasive uroflowmetry examination, measurement of post voiding residual (PVR), and measurement of cystometry (CMG).

Research hypothesis

Preurodynamic single-dose levofloxacin administration is more effective than posturodynamic levofloxacin for three days against UTI events.

Source

The data source of this research is primary data taken from patients who have indications for urodynamic examination at dr. Cipto Mangunkusumo Hospital, Siloam Asri Hospital, and Persahabatan Hospital during any given time.

Number of Samples

Calculation of the sample is made based on “*Dasar-dasar Metodologi Penelitian Klinis*” (Sastroasmoro et al.) regarding the calculation of proportions for 2 independent groups.¹⁴ From the literature, the effectiveness of posturodynamic prophylactic antibiotics in preventing UTI is 0.40 (P1). The effectiveness of levofloxacin 500mg preurodynamic single dose is believed to be 30% different from P1 (P2=0.70).

$$n_1 = n_2 = \frac{[Z_\alpha \sqrt{2PQ} + Z_\beta \sqrt{P_1Q_1 + P_2Q_2}]^2}{(P_1 - P_2)^2}$$

dimana $P = \frac{1}{2}(P_1 + P_2)$ dan $Q = 1-P$

$$n_1 = n_2 = \frac{[1,96\sqrt{2 \times 0,55 \times 0,45} + 0,842\sqrt{0,40 \times 0,60 + 0,70 \times 0,30}]^2}{(0,40 - 0,70)^2}$$

$$n_1 = n_2 = 41,6 \sim 42 \text{ pasien}$$

Considering the possibility of drop-out, it is decided that the number of samples taken is 100 patients, which will then be screened for eligibility and will be equally randomized.

Data Collection Technique

The data collection technique uses consecutive sampling method until the required number of subjects is reached.

The inclusion criteria in this study are:

- Male/female patients > 18 years who have indications for urodynamics
- Willing to participate in research

The exclusion criteria of this study are:

- Allergy to levofloxacin
- History of taking antibiotics in 1 month
- pregnant
- Uncontrolled DM
- Using a urinary catheter
- Having a UTI before urodynamics, based on clinical symptoms and urine examination results

- Refuse to participate in research

[figure not shown]
Statistical analysis technique

Descriptive exposure is used to assess the characteristics of the subject, such as age, sex, and indications for urodynamics. To assess the relationship between the incidence of UTI with the treatment group, chi-square analysis is used. The data will be processed using SPSS version 24 and is considered significant if $p < 0.05$.

Types of Research Activities

This research activity is experimental with the following research flow chart:

(next page)

Research Places

The research places are the urology outpatient clinic of the Urology Department, dr. Cipto Mangunkusumo Hospital and the Uronephrology Cluster of RSCM Kencana, Siloam Hospitals ASRI, and RSUP Persahabatan. At Siloam Hospitals ASRI, Prof. dr. [name], Sp.U(K), PhD will be in charge, while at the RSUP Persahabatan, the person in charge is dr. [name], Sp.U.

References

2. Nitti VW. Urodynamic and Video-Urodynamic Evaluation of the Lower Urinary Tract. Wein AJ, Kavoussi LR, Novick AC, Partin AW, Peters CA. *Campbell-Walsh Urology*. 10. Philadelphia, PA: Elsevier; 2012. 3: 1847- 1870.
9. EAU Guidelines. Edn. presented at the EAU Annual Congress Copenhagen 2018. ISBN 978-94-92671-01-1.

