Various studies show that a single episode of catheterization can increase the percentage risk of UTI by 2%. Meanwhile, the magnitude of post-procedure UTI infection according to several studies can range from 3-20% despite using good asepsis techniques. Several studies also show that gender is the most influential risk factor for the incidence of urinary tract infections after invasive procedures. With regard to the high rate of urinary tract infections associated with invasive procedures in the urinary tract, several guidelines suggest the use of antibiotics as prophylactic agents to prevent postoperative UTIs.

Levofloxacin as an antibiotic

Levofloxacin is a fluoroquinolone antibiotic with a broad spectrum of activity against Gram-positive and Gram-negative bacteria and atypical pathogens. Levofloxacin has antimicrobial effect against both penicillin-susceptible and penicillin-resistant *Streptococcus pneumoniae*. In America, the prevalence of *S. pneumoniae* resistance to levofloxacin is <1% overall. A number of studies have shown that levofloxacin is effective in treating infections of the respiratory tract, genitourinary tract, skin and integumental system. In one study comparing the administration of antibiotics in patients with nosocomial pneumonia, oral administration of levofloxacin 750 mg orally once daily for 7-14 days was equivalent to that of an intravenous imipenem/cilastatin regimen of 500-1000 mg every 6-8 hours followed by oral ciprofloxacin 750 mg. twice a day. In patients with community pneumonia (CAP), levofloxacin 500 mg intravenously and/or orally once daily for 7-14 days has a similar effect to regimens such as amoxicillin/clavulanic acid, clarithromycin, azithromycin, ceftriaxone and/or cefuroxime axetil and gatifloxacin. Oral levofloxacin is as effective as ofloxacin in uncomplicated urinary tract infections or equivalent to ciprofloxacin in the treatment of complicated urinary tract infections. In men with chronic bacterial prostatitis, levofloxacin 500mg orally once daily achieves levels equivalent to 500 mg orally ciprofloxacin twice daily. Compared with other quinolone antibiotics, levofloxacin is generally well tolerated. Some of the most commonly reported side effects include nausea and diarrhea; while some of the side effects that are often encountered with quinolones such as photosensitivity are also less common with the use of levofloxacin.¹¹

Use of Levofloxacin in the prevention of post-urodynamic UTI

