Although the evidence regarding the use of antibiotics after urodynamic examination varies, the experience of researchers in previous studies has shown that giving 3 doses of the antibiotic levofloxacin 500 mg can reduce the magnitude of the risk of post-urodynamic UTI by 55% compared to patients who do not receive prophylactic therapy at all.¹²

Pre-Urodynamic use of Levofloxacin for the prevention of UTI

Although prophylactic administration to prevent UTI after urodynamic examination using levofloxacin has not been studied before, there have been many studies that have tried to use various antibiotics such as augmentin, ciprofloxacin, cotrimoxazole, nitrofurantoin, norfloxacin, trimethopim, and cinoxacin as prophylactic therapy that can be given. And through a meta-analysis of these studies showed that the use of post-urodynamic prophylaxis can reduce the risk of infection by 40%.¹ Therefore, prophylaxis using antibiotics is also applied in several guidelines, especially if the conditions under which urodynamics are performed cannot be regulated in such a way as to achieve ideal conditions.¹³

[figure not shown]
Research methodology

This study is an experimental study with a single-blinded randomized clinical trial design to compare the proportion of UTIs in a group of patients receiving levofloxacin 500 mg single dose one hour before urodynamic examination and patients receiving levofloxacin 500 mg once daily for three days postoperatively-urodynamic examination. To determine the sample treatment group, blocked randomization technique is used in this study.

This study uses a single-blinded design because the outcome assessed in this study is urinalysis which is the objective outcome. The urinalysis evaluator is blinded to the drug regimen obtained by the research subjects.

An additional consideration for the use of a single-blinded design is the limited facility for making placebos.

Conceptual Framework

Definition of work

1. Single dose of Levofloxacin

Single-dose levofloxacin is defined as the administration of 500 mg of levofloxacin one hour prior to urodynamic procedures.

2. Levofloxacin for 3 days

Levofloxacin for 3 days is defined as the administration of levofloxacin 500 mg/day for 3 days post-urodynamic examination.

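### The sample size uses effectiveness values (0.40 and 0.70) where expected UTI proportions per arm are needed, so the implied 80% power is unsupported at the 3-20% UTI rates the protocol quotes

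*Combined protocol and SAP*

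**What the plan says.** The analysis compares UTI proportions. Under Statistical analysis technique: "To assess the relationship between the incidence of UTI with the treatment group, chi-square analysis is used". The Research methodology section describes the comparison in the same way.

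The Number of Samples section uses the standard formula for two independent proportions, with these inputs:

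- Three-day arm: "From the literature, the effectiveness of posturodynamic prophylactic antibiotics in preventing UTI is 0.40 (P1"). No reference is attached to the figure.
- Single-dose arm: "The effectiveness of levofloxacin 500mg preurodynamic single dose is believed to be 30% different from P1 (P2=0.70").
- Z-values of 1.96 and 0.842, giving a printed 41.6, rounded to 42 per arm.
- To allow for drop-out, "the number of samples taken is 100 patients, which will then be screened for eligibility and will be equally randomized".

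The background sections give three related figures:

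- Pre-Urodynamic use of Levofloxacin: a "meta-analysis of these studies showed that the use of post-urodynamic prophylaxis can reduce the risk of infection by 40" per cent.
- Use of Levofloxacin in the prevention of post-urodynamic UTI: three doses of "levofloxacin 500 mg can reduce the magnitude of the risk of post-urodynamic UTI by 55" per cent.
- Epidemiology of UTI on urodynamic examination: "the magnitude of post-procedure UTI infection according to several studies can range from 3-20% despite using good asepsis techniques".

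The endpoint is broad: "Urinary tract infection is defined based on the results of urinalysis in which one of the following conditions is present" (leukocyturia, bacteria, nitrite or leukocyte esterase). The Abstract (Research Method) gives the type 2 error as 80%.

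**The concern.** A two-proportion formula needs the quantity that the test will compare. Here that is the expected proportion with UTI, or equivalently without UTI, in each arm. The plan states neither. Its 0.40 and 0.70 are labelled effectiveness, and the most likely source of the 0.40 is the meta-analytic 40% risk reduction. That link is an inference, but no other 40% effect of prophylaxis appears in the document. For the actual comparator, three-day levofloxacin, the document quotes 55%, which is not used. The 0.70 rests on belief alone.

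The 42 per arm depends on a 30-point gap in proportions that no quoted UTI rate supports. If actual rates are near those quoted, a moderate or even large true difference could easily be missed. A non-significant p-value could then be read as an 80%-powered finding that the regimens do not differ. The Abstract says the results may guide the choice of regimen, and no confidence interval is planned to show the uncertainty.

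**Working it through.** **1. The plan's own figure.** With P = (0.40 + 0.70)/2 = 0.55 and Q = 0.45:

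n = [1.96 × √(2 × 0.55 × 0.45) + 0.842 × √(0.40 × 0.60 + 0.70 × 0.30)]² / 0.30²

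= (1.3790 + 0.5648)² / 0.09 = 41.98, so 42 per arm.

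The printed 41.6 is a small slip that rounds to the same number. Z = 0.842 corresponds to a 20% type 2 error. A literal 80% (Z = −0.842) would give 7.4 per arm, so 42 was computed at 80% power.

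**2. What the inputs could mean.**

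- *UTI-free proportions.* UTI would be 60% (three-day) versus 30% (single dose), both above 3-20%.
- *UTI proportions.* UTI would be 40% versus 70%, with single dose worse, against the stated hypothesis.
- *Relative risk reductions.* These need an untreated risk R, giving arm rates of 0.6R and 0.3R. The formula then returns 42 per arm only if R = 100%. At R = 50% (30% versus 15%) it returns 121.

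If the three-day rate is 20% or lower, a 30-point reduction is arithmetically impossible.

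**3. Power at plausible rates.** This is exact power of the uncorrected Pearson chi-square test at two-sided 0.05, by full binomial enumeration. Rates are three-day versus single dose. Fifty per arm is a ceiling, because the 100 patients are counted before eligibility screening. All rows are scenarios, not bounds.

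| Assumption | UTI rates | 42/arm | 50/arm |
|---|---|---|---|
| Plan's inputs as UTI-free proportions | 60% vs 30% | 82.8% | 87.6% |
| Untreated 3%, reductions 40% and 70% | 1.8% vs 0.9% | 0.5% | 0.8% |
| Untreated 10%, same reductions | 6% vs 3% | 8.5% | 9.2% |
| Untreated 20%, same reductions | 12% vs 6% | 17.6% | 17.6% |
| Untreated 20%, reductions 55% and 70% | 9% vs 6% | 9.1% | 8.0% |
| Untreated 20%, reductions 55% and 85% (30-point gap kept) | 9% vs 3% | 21.8% | 22.2% |
| Three-day rate 20%, halved | 20% vs 10% | 25.9% | 30.3% |
| Three-day rate 20%, cut by 70% | 20% vs 6% | 51.4% | 58.4% |
| Widest pair within 3-20% | 20% vs 3% | 76.7% | 81.8% |
| Broad definition raises rates, halved | 30% vs 15% | 38.6% | 44.3% |
| Higher still, halved | 40% vs 20% | 52.4% | 59.5% |

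**4. What 80% power would require.**

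- With 20% in the three-day arm, the single-dose rate must be about 2.6% or less (42 per arm) or 3.2% or less (50 per arm). That is a reduction of (20 − 2.6)/20 = 87% or (20 − 3.2)/20 = 84%.
- If single dose halves the rate, the three-day rate must be about 58% (42 per arm) or 54% (50 per arm).
- The plan's formula gives 199 per arm for 20% versus 10%, and 89.4, so 90 per arm, for 20% versus 6%.

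**5. Precision.** At 20% versus 10%, the approximate 95% half-width for the difference is 1.96 × √[(0.20 × 0.80 + 0.10 × 0.90)/n]. This is 15.1 points at 42 per arm and 13.9 at 50. Both exceed the 10-point difference itself.

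**The case against.** The strongest reply is that actual power is unknown rather than shown to be low. The 3-20% range is tied to no UTI definition and to no prophylaxis status. The trial counts any single urinalysis sign, which is broader than the document's own confirmed UTI (pyuria with bacteriuria), so event rates may be well above 20%. If they are, and the 30-point gap is real, power is adequate: 40% versus 10% gives 92% and 95% at 42 and 50 per arm, and 50% versus 20% gives 84% and 89%. Effectiveness could also mean the proportion free of UTI, which is a valid input because the formula is symmetric. The fault would then be an unsupported assumption rather than a wrong quantity.

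Much of this stands as a caution. The source of the 0.40 is inferred, and the relative-risk rows depend on that inference. The 55%/85% pairing is a construction. In the rows with untreated risks of 3-20%, expected UTI counts are below 5 per arm, so the uncorrected chi-square is itself doubtful and the near-zero powers partly reflect the test. At a full 50 per arm, the extreme 20% versus 3% pair does just exceed 80%.

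None of it supplies the missing input. The document gives no rate under its own definition, so the favourable scenarios are as unsupported as the unfavourable ones. Nor does it plan an equivalence claim, but a superiority hypothesis does not stop a non-significant result being misread.

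**Conclusion.** The concern holds. The plan tests UTI proportions but sizes the trial on effectiveness values, and no reading of those values gives arm rates that the document supports. At the calculated 42 per arm, no pair of rates inside 3-20% reaches 80% power; the best is 76.7%. A halving from 20% would be detected about 26-30% of the time.

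That no per-arm UTI proportion is stated, and that the calculation therefore does not support 80% power, is certain from the text. The specific power figures are conditional on the assumed rates, chiefly that 3-20% is relevant to this endpoint. The abstract's 80% type 2 error is a separate wording slip that did not affect the 42.

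**What to change.** 1. In Number of Samples, replace P1 and P2 with the expected UTI proportion in each arm under the trial's own definition. Name the source of each and label what is assumed.
2. Keep the planned 100 patients. Replace the implied 80% with the power that number delivers over a labelled range of rates, such as the table above. Include higher-rate scenarios if the broad definition is expected to raise rates, and note where expected counts fall below 5.
3. In Statistical analysis technique, report the difference in UTI proportions with a 95% confidence interval beside the chi-square p-value. State that a non-significant result is not evidence that the regimens are equivalent.
4. In the Abstract, correct the type 2 error of 80% so that it agrees with the revised power statement.

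The cost is a rewritten sample-size section, one phrase in the Abstract and one added interval. The stated power will look less favourable. No extra patients are needed and the primary test is unchanged.

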Comparison of the Effectiveness of Preurodynamic Single Dose Levofloxacin with Posturodynamic Levofloxacin for Three Days on the Incidence of Urinary Tract Infections

[name]
[name]
[name]
[name]

NCT Number:
NCT05219877

January 10th, 2022
Department of Urology
RSUPN dr. Cipto Mangunkusumo

Research Title

Comparison of the Effectiveness of Preurodynamic Single Dose Levofloxacin with Posturodynamic Levofloxacin for Three Days on the Incidence of Urinary Tract Infections

Abstract

a) Study aims

This study aims to compare the effectiveness of preoperative single dose of levofloxacin with postoperative levofloxacin for three days on the incidence of urinary tract infections (UTI) after urodynamic examination.

b) Research Method

This study uses a randomized single-blind trial design to compare the proportion of posturodynamic UTI in the group receiving preurodynamic single-dose levofloxacin with the group receiving three days posturodynamic levofloxacin. The target population is patients who undergo urodynamic examination at the RSUPN dr. Cipto Mangunkusumo during any given time. The total sample size in this study is determined based on a two-proportion analytical sample calculation formula with type 1 error of 5% and type 2 error of 80%. On the fourth posturodynamic day, urinalysis and urine culture are performed to determine the diagnosis of UTI. To analyze the association between UTI and the treatment group, the chi-square test is used. Results are considered statistically significant if $p < 0.05$.

c) Expected Results

The expected result is data on the comparison of the incidence of UTI after urodynamic examination in the group given a single dose of levofloxacin and levofloxacin for three days after the examination.

d) Outcome

The incidence of UTI in the group receiving a single preurodynamic dose of levofloxacin compared to the group receiving levofloxacin for three days posturodynamics.

e) Benefit

By obtaining data on the comparison of the effectiveness of a single preurodynamic dose of levofloxacin and levofloxacin for three days posturodynamics on the incidence of UTI after a urodynamic examination, it can be used as a basis for selecting a therapeutic regimen to prevent the occurrence of posturodynamic UTI. This can directly contribute to quality improvement, namely the reduction of antibiotic resistance rates and savings in service costs at dr. Cipto Mangunkusumo Hospital

Background

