The most widely used classification of urinary tract infections (UTIs) is the classification developed by the CDC, IDSA, ESCMID, and the US FDA. As adjusted for EAU guidelines, UTI can be classified according to clinical features, anatomic location, severity of infection, categorization of comorbid risk factors and presence of therapy.⁹

The following is a UTI classification adapted from the EAU guidelines:⁹

UTI Classifications	
Non-complicated UTI	Acute, sporadic or recurrent infections of the lower and/or upper urinary tract, affecting nonpregnant women, postmenopausal women without anatomic abnormalities and comorbidities of the urinary tract
Complicated UTI	All UTIs that cannot be classified as non-complicated. In other words, UTI is in patients with a higher risk of complications, such as: men, pregnant women, patients with anatomic or functional abnormalities of the urinary tract, and/or with other coexisting immune disorders such as diabetes or HIV.
Recurrent UTI	Recurrent non-complicated and/or complicated UTI with a frequency of at least 3 times a year or 2 times in the last 6 months.

Catheter-related UTI	Catheter-related UTI refers to UTI that occurs in patients who use repeated/routine catheters and have used a catheter for at least the last 48 hours.
Urosepsis	Urosepsis is defined as life-threatening organ dysfunction resulting from dysregulation of the supervisor's response to infections originating in the urinary tract and/or male reproductive organs.

And these followings are the common terminology used to describe UTI clinically.¹⁰

Terminologi	Definisi
Pyuria	Presence of >10 white blood cells/mm ³ per large visual field
Bacteriuria	>10 ⁵ colony-forming of urinary pathogens units per mL
Confirmed UTI	Pyuria accompanied by bacteriuria
Asymptomatic bacteriuria	Presence of bacteriuria in the absence of genitourinary symptoms/signs

Asymptomatic bacteriuria

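### The baseline exclusion cites symptoms and urine results while the outcome needs one urinalysis finding, so on a literal reading pre-existing findings can count as new UTI

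*Combined protocol and SAP*

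**What the plan says.** All references are to the combined protocol and SAP.

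- **Exclusion criteria (Data Collection Technique).** Patients are excluded for "Having a UTI before urodynamics, based on clinical symptoms and urine examination results". No urinalysis threshold is given, and there is no reference back to the study's own definition of UTI.
- **Operational definition (Definition of work, item 3).** "Urinary tract infection is defined based on the results of urinalysis in which one of the following conditions is present": leukocyturia above 5 per field, bacteria, nitrite or leukocyte esterase. Symptoms play no part.
- **Outcome.** Research methodology states that "the outcome assessed in this study is urinalysis which is the objective outcome". The Abstract gives the timing and adds culture: "On the fourth posturodynamic day, urinalysis and urine culture are performed to determine the diagnosis of UTI".
- **Allocation and analysis.** "To determine the sample treatment group, blocked randomization technique is used in this study". The only comparison is unadjusted: "To assess the relationship between the incidence of UTI with the treatment group, chi-square analysis is used".
- **Size.** Number of Samples derives 42 per arm and then states that "the number of samples taken is 100 patients, which will then be screened for eligibility and will be equally randomized".

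The readable text does not make normal urine a condition of entry, and it does not require the day-4 finding to be new.

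**The concern.** The same word, UTI, appears to be applied by different rules at entry and at outcome. The entry rule joins symptoms and urine results with an *and*; the outcome rule needs one urine finding. A patient with, say, leukocyturia and no complaints before the procedure would pass the entry rule read literally. If the leukocyturia is unchanged on day 4, that patient is an event.

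The trial describes its endpoint as the incidence of UTI after urodynamics and is meant to guide the choice of prophylaxis. If pre-existing findings enter the count, the event rate no longer measures what the procedure caused or the drug prevented, and the difference between arms shrinks towards zero. The protocol itself describes symptom-free bacteriuria as common. It also names several recruiting hospitals, so screeners could apply the criterion differently.

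**Working it through.** **1. The plan's own figure.** Inputs from Number of Samples: P1 = 0.40, P2 = 0.70 (proportions in whom UTI is prevented), Zα = 1.96, Zβ = 0.842.

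n = [1.96·√(2 × 0.55 × 0.45) + 0.842·√(0.40 × 0.60 + 0.70 × 0.30)]² / 0.30² = (1.3790 + 0.5648)² / 0.09 = 41.98, so 42 per arm. The protocol prints 41.6, which rounds up to the same 42. The point here does not challenge this figure.

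**2. Power formula.** This is the inverse of the same formula: power = Φ[(d − 1.96·se₀)/se₁], with d the difference in event rates, se₀ the pooled and se₁ the unpooled standard error. Reading P1 and P2 as UTI-free proportions, the event rates are 60% and 30%. Power is 80.0% at 42 per arm and 86.6% at 50 per arm.

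**3. Adding baseline positives (assumed).** Let b be the share entering with abnormal urine and s the fraction of those still positive on day 4, equal in both arms. Those who clear carry the ordinary risk p. Then:

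observed rate q = b·s + (1 − b·s)·p.

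Worked case, b = 10%, s = 1:
- q₁ = 0.10 + 0.90 × 0.60 = 0.64; q₂ = 0.10 + 0.90 × 0.30 = 0.37; d = 0.27 instead of 0.30.
- At 42 per arm, se₀ = √(2 × 0.505 × 0.495/42) = 0.1091 and se₁ = √((0.64 × 0.36 + 0.37 × 0.63)/42) = 0.1051.
- Power = Φ[(0.27 − 1.96 × 0.1091)/0.1051] = Φ(0.535) = 70.4%.

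The share of counted events that predate the procedure is 2bs/(q₁ + q₂). For the worked case this is 0.20/1.01 = 19.8%.

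| b·s | Example | Event rates | Power, 42/arm | Power, 50/arm | Pre-existing share |
|---|---|---|---|---|---|
| 0 | none | 60.0% v 30.0% | 80.0% | 86.6% | 0% |
| 2.5% | b = 10%, s = 0.25 | 61.0% v 31.8% | 77.7% | 84.6% | 5.4% |
| 5% | b = 10%, s = 0.5 | 62.0% v 33.5% | 75.3% | 82.4% | 10.5% |
| 10% | b = 10%, s = 1 | 64.0% v 37.0% | 70.4% | 77.9% | 19.8% |
| 20% | b = 20%, s = 1 | 68.0% v 44.0% | 60.4% | 68.1% | 35.7% |

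The share also depends on the event rates. If they were 20% v 10% instead (an assumption; the protocol's literature section cites 3-20% post-procedure UTI), b·s = 5% gives 0.10/(0.24 + 0.145) = 26.0% and b·s = 10% gives 0.20/(0.28 + 0.19) = 42.6%.

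**4. What the documents say about b and s.** They give no prevalence for patients referred for urodynamics. Their asymptomatic bacteriuria ranges run from 1-5% (premenopausal women) through 4-19% (elderly) to 23-89% (spinal disorders), and neurogenic bladder dysfunction is a listed indication. These are culture-based figures, while the outcome is urinalysis. The exclusions for catheter use, recent antibiotics, pregnancy and uncontrolled diabetes may lower b. No persistence rate is given. The nearest figure is that 49.6% of urinary *E. coli* isolates, mostly from inpatients, were sensitive to levofloxacin; it does not set s.

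**5. Restricting to baseline-negative patients.** With b = 10%, 100 patients leave 90, or 45 per arm, and power is 82.8%. Keeping everyone (50 per arm) gives 84.6%, 82.4% or 77.9% for s = 0.25, 0.5 or 1. Restriction therefore costs 1.8 points, gains 0.4 or gains 4.9; break-even is at s ≈ 0.46.

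**The case against.** The strongest reply is that the text has a natural reading with no defect. UTI is an operationally defined term based on urinalysis, the exclusion reuses it, and the reference to symptoms and urine results may simply list the sources a screener consults. The flow charts are not shown and could specify baseline urine screening. This stands as a real possibility, and it is why the point is a contradiction to reconcile rather than a proven error. It does not remove the point: if the definition governed, the mention of symptoms would add nothing, and no readable sentence makes the link.

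Several stronger readings are tempting and should be resisted.

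- *The protocol's own terminology table shows that symptoms are required.* The table lists asymptomatic bacteriuria separately ("Presence of bacteriuria in the absence of genitourinary symptoms/signs"), but it defines confirmed UTI as pyuria with bacteriuria, also without symptoms. It supports admitting isolated bacteriuria at most, and it is literature review, not an eligibility rule.
- *The comparison is biased.* Blocked randomisation balances baseline positives on average. Distortion of the prevention question would need unequal clearance between the arms. The regimens differ, so this is conceivable, but the documents do not quantify it. Chance imbalance is possible at 42 to 50 per arm.
- *The trial is underpowered.* With 50 per arm, power stays above 80% in the milder cases. Whether 50 per arm will be reached is unclear, because the 100 are described as screened after being taken.
- *The 19% for the elderly is a ceiling on prevalence.* The range for spinal disorders lies above it, so no upper bound is claimed.

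**Conclusion.** The point holds as a mismatch between two stated rules that bears on the primary endpoint. Followed literally, the plan admits symptom-free patients with abnormal urine and counts a persisting finding as an incident UTI. The expected consequence is an endpoint mixing old and new findings and a diluted difference.

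At an assumed b·s of 5% to 10%, the loss is about 5 to 10 points of power at 42 per arm and 4 to 9 points at 50 per arm. About a tenth to a fifth of counted events would predate the procedure at the protocol's event rates, and more if the true rates are lower. These sizes rest on assumed prevalence, assumed equal persistence and the 60% v 30% reading of P1 and P2, and they apply only on the literal reading. Priority is low to moderate: the first need is to settle which reading applies.

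**What to change.** Reconcile the two statements in one of two ways.

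1. **At entry.** Apply the outcome's urinalysis definition, regardless of symptoms, to the baseline urine examination the exclusion already refers to, on urine collected before any study drug.
2. **At outcome.** Define the primary event as new-onset (baseline negative, day-4 positive) and compare the arms among baseline-negative patients.

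In either case, restate power for the resulting evaluable number, and say whether 100 is the number screened or the number randomised.

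The cost is one sentence and a smaller analysis set: about 90 of 100 at 10% baseline positives (82.8% power before other losses), with a small loss of power if fewer than about half the findings persist. If urine was in practice to be examined only in patients with symptoms, testing everyone at baseline would be additional work; the exclusion as written suggests it is already planned. The gain is mainly one of meaning: the endpoint would measure new UTI after the procedure, as its name says.

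### Sex is named as the leading risk factor for UTI and is recorded, but the only planned comparison ignores it; prespecifying a sex-stratified analysis would be a cheap improvement

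*Combined protocol and SAP*

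**What the plan says.** All references are to the combined protocol and SAP.

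- **Epidemiology of UTI on urodynamic examination:** "Several studies also show that gender is the most influential risk factor for the incidence of urinary tract infections after invasive procedures". The sentence carries no reference number and no effect size.
- **Data Collection Technique:** both sexes are eligible: "Male/female patients > 18 years who have indications for urodynamics". No quota by sex is stated.
- **Statistical analysis technique:** sex is recorded for description only: "Descriptive exposure is used to assess the characteristics of the subject, such as age, sex, and indications for urodynamics". The treatment comparison follows: "To assess the relationship between the incidence of UTI with the treatment group, chi-square analysis is used".
- **Abstract, Research Method:** the same single test appears: "To analyze the association between UTI and the treatment group, the chi-square test is used".
- **Research methodology:** "To determine the sample treatment group, blocked randomization technique is used in this study". No stratification factor is named.

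No visible text plans an analysis stratified by sex or adjusted for it.

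**The concern.** The plan names what it regards as the strongest predictor of its outcome, collects it, and leaves it out of the comparison. With 42 to 50 patients per arm and no stratification by sex in the text, a visible chance difference in the share of women is quite possible. If sex also strongly predicts the outcome, the crude difference between regimens then contains part of the sex difference, and the planned analysis would not show how much.

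An adjustment could still be made afterwards, but it would be chosen with the sex split, and probably the result, already known. A reader could not tell whether it had been chosen for its answer. What is missing is a sex-stratified result fixed in advance.

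**Working it through.** **1. The plan's own figure.** Number of Samples uses P1 = 0.40, P2 = 0.70, Zα = 1.96 and Zβ = 0.842:

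n = [1.96√(2×0.55×0.45) + 0.842√(0.40×0.60 + 0.70×0.30)]² / 0.30² = 41.98, so 42 per arm.

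The plan prints 41.6, which rounds to the same 42. The abstract's "type 1 error of 5% and type 2 error of 80" percent is read as 80% power, because that is what 0.842 gives. With 100 patients equally randomised there are at most 50 per arm. Nothing below changes the sample size.

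**2. Assumptions.** P1 and P2 are described as effectiveness in preventing UTI, so UTI risk is taken as 1 − 0.40 = 0.60 (three-day arm) and 1 − 0.70 = 0.30 (single-dose arm), with mean 0.45. The documents give no sex ratio and no sex-specific risk. A 50:50 mix and a common sex odds ratio of 1, 2, 3 or 5 are assumed, with women as the higher-risk sex for illustration. Rejection probabilities are exact enumerations at two-sided 0.05, for the uncorrected Pearson chi-square and the uncorrected CMH test.

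**3. How often an imbalance arises.** For a gap of at least 8 women between arms of 42:

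- independent Binomial(42, 0.5) counts: 10.1%
- fixed totals of 42 women and 42 men (hypergeometric): 12.6%
- binomial with 60% or 70% women: 9.4% or 7.3%

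**4. What it does to the crude difference.** Under the null, the expected shift at 25 v 17 is (25 − 17)/42 × (risk in women − risk in men). At mean risk 0.45 and odds ratio 3 the sex-specific risks are 0.583 and 0.317, so the shift is 0.190 × 0.266 = 5.1 points, against a planned difference of 30.

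**5. Type I error given 25 v 17, mean risk 0.45.**

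| Sex odds ratio | Crude | Crude at exact balance (21 v 21) | CMH |
|---|---|---|---|
| 2 | about 7.0% | 5.8% | about 5% |
| 3 | 8.1% | 5.2% | about 5% |
| 5 | 10.0% | 4.3% | about 5% |

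At lower risks the excess is smaller. For sex-specific risks of 45%/15%, 18%/6%, 40%/25% and 16%/8.7%, crude type I error is 7.5%, 6.5%, 5.7% and 5.9%, and CMH is 4.9-5.1%.

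**6. Power given the same split, UTI risks 0.60 v 0.30.** The first crude figure applies when the three-day arm has the 25 women, the second when the single-dose arm has them.

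| Sex odds ratio | Crude | CMH |
|---|---|---|
| 1 | 82.8% in both | 78.7% |
| 2 | 89.4% or 74.8% | 79.5-80.3% |
| 3 | 92.5% or 69.8% | 81.1-81.9% |
| 5 | 95.6% or 63.3% | 83.8-84.8% |

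**7. Averaged over all allocations.**

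| Per arm | Crude power | CMH power at odds ratio 1 / 2 / 3 / 5 | Crude size at risk 0.45 |
|---|---|---|---|
| 42 | 82.8% | 79.4 / 80.6 / 82.2 / 85.1% | 6.2% |
| 50 | 87.6% | 86.5 / 87.1 / 88.4 / 90.6% | 5.6% |

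CMH size is 4.9-5.2%. When sex has no effect, the CMH cost is 82.8 − 79.4 = 3.4 points at 42 per arm and 87.6 − 86.5 = 1.1 at 50. Part of this arises because the crude test runs above its nominal 5%. CMH is ahead on average from an odds ratio of about 3 at 50 per arm, and from somewhere between 3 and 5 at 42.

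**The case against.** An unadjusted chi-square of a binary outcome is a complete and legitimate primary analysis of a randomised trial, and the protocol promises nothing by sex. That stands. A reader might infer from the background sentence that the crude test is biased or invalid; the documents do not support this. Averaged over allocations, crude type I error is the same with or without a sex effect: about 5% at mean risk 30% and 5.7% at 12%.

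The premise is also thin. It is one unreferenced sentence about invasive procedures in general. The trial's outcome is any one of several urinalysis findings (Definition of work, item 3), in patients screened free of UTI and urinary catheters. The size of the benefit therefore cannot be shown from the documents, and every figure that depends on sex is conditional on assumptions.

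CMH as primary can lose power, as step 7 shows. At 25 v 17 with no sex effect the loss is 82.8 − 78.7 = 4.1 points. This is a fair argument for keeping the crude test primary and CMH as support, which costs no power. It does not argue against prespecifying CMH.

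A reader might also infer that separate tests in men and women are needed. They are not: with one sex making up 30-70% of patients, power within that sex for the planned effect is about 32-64% at 42 per arm and 37-72% at 50.

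Finally, the study figures are missing from the text as read, so strata shown only there cannot be excluded. The written analysis would still be unstratified.

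**Conclusion.** The point holds as a low-cost improvement worth considering. The plan calls sex the leading risk factor, records it, and prespecifies no analysis that uses it. The crude chi-square remains valid on average.

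The benefit is protection in the roughly one trial in eight to ten with a split of 25 v 17 women or worse. In such a trial the crude type I error would be about 7-10% at mean risk 0.45 and sex odds ratios of 2 to 5, and 5.7-7.5% in the lower-risk scenarios. Crude power at odds ratio 3 would depend on the direction of the imbalance by about 23 points (92.5 − 69.8), where CMH moves by less than one. The excess rises gradually with the sex effect and also depends on the baseline risk, so no single odds ratio marks where it begins to matter.

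All of this rests on the assumed 50:50 mix, the assumed sex effects and the reading of UTI risk as one minus effectiveness.

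**What to change.** In Statistical analysis technique, and in the matching line of the abstract's Research Method:

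- Prespecify a CMH test of UTI by treatment group stratified by sex, without continuity correction. The correction would cost about 7 further points of power at 42 per arm (72.5% when sex has no effect) and 4-5 at 50.
- Report the Mantel-Haenszel risk difference with its 95% CI.
- Report the crude chi-square alongside.
- State now which of the two is primary, so that the choice cannot depend on the observed sex split.

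The change is to wording: sex is already collected, and no extra patients or visits are needed. The team should confirm that the named software (SPSS version 24) gives the uncorrected test and the risk difference, or name how they will be computed. If CMH is primary and sex has no effect, the cost is about 3.4 points of average nominal power at 42 per arm and about 1 point at 50. If CMH is a prespecified supporting analysis, there is no power cost.
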